- This proposal is a subproject of a currently approved study (PI, [name]), titled “A Patient-centered Intervention Using Technology to Reduce Colorectal Cancer Disparities in Primary Care” (1R01CA207689-01A1) (IRB#201702765 and IRB#201601642). The goal of the parent project is to test the efficacy of a patient-centered, tailored message intervention for increasing CRC screening among racial minorities and rural patients. Given the challenges of discussing nutritional risk in a clinical setting, the objective of this proposed subproject is to test if tailored nutrition-risk information delivered in a web-based platform increases perceptions of CRC risk and CRC prevention behaviors.

2. Specific Aims:

- The goal of this proposed project is to adapt an existing CRC screening intervention to include a nutrition module that engages users with information about alcohol and red/processed meat consumption, and delivers tailored nutrition-risk messages to enhance CRC prevention outcomes.
- The objective of this proposed project is to pilot test the adapted VHT-delivered, tailored, nutrition-risk module to investigate mechanisms of efficacy for the adapted intervention including establishing preliminary estimates for CRC risk perceptions and CRC prevention behaviors. This information will be used to inform a larger trial.
- The hypothesis is reporting dietary intake and receiving personalized nutrition-risk factors for CRC via a VHA will increase perceptions of CRC risk, CRC screening intentions, and information seeking behaviors (e.g. reducing alcohol, red/processed meat, how to order at home screening kit).
- **Aim 1:** Modify an existing CRC intervention with a nutrition module where VHAs collect dietary intake information and give tailored visual feedback on nutrition risk factors for CRC. To increase patient engagement with nutrition-risk messages delivered in a virtual setting, we must first understand beliefs, experiences, and evaluations of nutrition-risk communication. We will engage in a cultural adaptation of an interactive nutrition module delivered by virtual health assistants (VHAs) to ensure acceptable social reactions to reporting dietary intake of alcohol and red/processed meat and receiving personalized feedback in the virtual setting. We will also conduct content adaptation of the module (tailoring language, visuals, and examples of food items).

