- **Aim 2:** Pilot test the VHA intervention to assess if the tailored nutrition module increases (2a) accurate risk perceptions for CRC (2b) intentions to screen for CRC (2c) and information seeking behaviors (e.g. how to reduce alcohol and red/processed meat intake, how to order home screening kit).

3. Research Plan / Study Description:

Aim 1

Eligibility Criteria:

- Eligible adults will be between 50-73 years old, proficient in English and geographically rural areas of north central Florida. We will enroll black, white, male and female participants.

Focus Group Structure:

- Adults at risk for CRC will participate in focus groups with an estimated 6 groups comprised of approximately 6 people. (N=36)
- Focus groups will be conducted via an iterative cycle of adaptation based on participant feedback:
 - Cycle 1: FG 1 and 2 use storyboard exercise and discussion to inform initial content and message preferences for nutrition module → PI meet with graphic designer/VH team to develop initial prototype
 - Cycle 2: FG 3 and 4 comment on developed first round stimuli from graphic designer/first prototype of module → PI meet with graphic designer/VH team to modify module
 - Cycle 3: FG 5 and 6 comment on module version 2 → PI meet with graphic designer/VH team to update
- Focus groups will take place in the community at an accessible location, take approximately two hours, and will be video and audio-recorded.
- Due to Covid-19, as of Fall 2020 we will be conducting focus groups via zoom.
- Trained researchers will conduct the focus groups using a semi-structured guide based on the Cultural Sensitivity Model (Resnicow, 2000).
- Participants will answer questions to inform acceptability of messages and graphics to be delivered in the virtual setting related to CRC risk. Participant responses will help adapt the VHT nutrition module for cultural appropriateness, content, and framing of nutrition communication.
- A questionnaire assessing participant characteristics, perceptions, and behaviors will also be administered.

Individual Think-aloud Interview Structure:

- A usability test of the nutrition module will be achieved by conducting individual, in audio and video-recorded think-aloud interviews (N=12) rooted in user-centered design principles.
- Due to Covid-19, as of Fall 2020 we will be conducting interviews via zoom.
- Think-aloud interviews will continue using the iterative process:

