- We will pilot-test the module using a 3-group randomized design with 30 participants per group. Participants will be randomized to one of three groups: 1) high interactive VHA administered nutrition module, 2) low interactive VHA module, or 3) attention control module. Each module will be approximately 5-10 minutes.
- For group 1, the VHA will interactively collect nutrition information (alcohol, red meat, and processed meat intake) and report risk information back to users in visual and audio format. Group 2, will complete the current intervention module that includes items assessing alcohol and meat intake.

This module is consistent with [name] ongoing clinical trial work. Groups 1 and 2 will receive CRC prevention messages including information about how to use a home FIT screening test (delivered by the VHA).

- Group 3, the attention control group, will complete a non-CRC related module (e.g. recycling).
- All groups will complete a questionnaire assessing outcomes of interest and participant characteristics.
- All participants will access the intervention using an electronic link sent to them via email.
- Participants will have option to receive additional information (see outcome 3 below). Those participants will be directed to evidence-based cancer prevention resources housed on the secure web platform Wix.com.

Data and analysis:

- We will assess three main outcomes variables:
- (1) Accurate risk perceptions for CRC (e.g. items measured on a 7-point Likert scale, "My chance of getting CRC are high", "FIT screening decreases my chances of dying from cancer").³⁰
- (2) Intentions to screen for CRC (e.g. items measured on a 7-point Likert scale "I want to get screened for colon cancer" or "I will talk to my doctor about colon cancer screening with FIT").³¹
- (3) Information-seeking behavior (e.g. assessed via clicks on links regarding "reducing alcohol/meat consumption", "how to order a FIT kit" (for intervention groups) or "tips for recycling" (for attention control group). We will use the Qualtrics "event tracking" feature to track clicks (yes/no).
- For outcomes (1) and (2) we will conduct one-way ANOVAS or Kruskal-Wallis test on the difference between baseline and post-test to obtain estimates to inform the larger trial.
- For outcome (3) we will use Pearson's chi-square test or Fisher exact test.

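### Aim 2 has no pre-specified between-arm estimate: outcomes 1 and 2 get only omnibus tests, and outcome 3 does not say which groups are compared although Group 3's link is about recycling

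*Combined protocol and SAP*

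**What the plan says.** Section 2 (Specific Aims) states Aim 2 as "Pilot test the VHA intervention to assess if the tailored nutrition module increases (2a) accurate risk perceptions for CRC", followed by screening intentions (2b) and information seeking (2c). Neither the aim nor the hypothesis names a comparator arm. The same section describes the project this way: "The goal of this proposed project is to adapt an existing CRC screening intervention to include a nutrition module".

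Section 3, Aim 2, Pilot Test Structure, randomises 30 participants to each of three arms: a high interactive nutrition module (Group 1), a low interactive module (Group 2) and a non-CRC attention control (Group 3). Group 2 "will complete the current intervention module that includes items assessing alcohol and meat intake". On shared content it says "Groups 1 and 2 will receive CRC prevention messages including information about how to use a home FIT screening test". Group 3 does not receive these messages.

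Under Data and analysis, the plan is "For outcomes (1) and (2) we will conduct one-way ANOVAS or Kruskal-Wallis test on the difference between baseline and post-test", with the stated purpose of obtaining estimates for the larger trial. For clicks it is "For outcome (3) we will use Pearson's chi-square test or Fisher exact test". The example links are diet and FIT-kit links for the intervention groups and a recycling-tips link for the attention control group.

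The same section later plans confidence interval estimates and descriptive statistics. It attaches them to no arm, difference or effect measure.

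**The concern.** One-way ANOVA and Kruskal-Wallis ask whether any group differs from any other. Group 3 differs from both other arms in the CRC and FIT messages as well as in the nutrition content. A significant result could therefore mean that the new module adds something to the current one, or only that any CRC module differs from a recycling module. Aim 2 needs those two answers kept apart. The larger trial also needs a difference to carry forward, and the plan leaves open whether that is Group 1 minus 2, Group 1 minus 3, or Groups 1 and 2 pooled minus 3. The choice could then be made after the data are seen.

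For outcome 3 the problem is one of validity. If all three groups enter the test, which is the natural reading, the event counted differs by arm: a click on a diet or FIT link in Groups 1 and 2, a click on a recycling link in Group 3. The p-value could then reflect interest in the topic of the link and not an effect of the module.

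**Working it through.** **Inputs.** From the protocol: three arms, 30 per arm, and an expected small effect of .1 to .3 (sample-size paragraph, Aim 2 Data and analysis). The total reproduces: 3 × 30 = 90. The 25 per arm comes from a cited rule of thumb whose table is not in the document, so it cannot be re-derived; nothing below depends on it. Assumed, because the plan is silent: two-sided alpha 0.05; .1 to .3 read as SD units of the change score; all click rates.

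**Outcomes 1 and 2, ANOVA.** Noncentrality is λ = n Σ(μᵢ − μ̄)².
- Groups 1 and 2 both move by d, Group 3 does not (d, d, 0): μ̄ = 2d/3, and Σ = d²/9 + d²/9 + 4d²/9 = 2d²/3.
- Only Group 1 moves (d, 0, 0): μ̄ = d/3, and Σ = 4d²/9 + d²/9 + d²/9 = 2d²/3.

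In both patterns λ = 30 × 2d²/3 = 20d². In the first the new module adds nothing to the current one; in the second it adds d. With 2 and 87 degrees of freedom:

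| d (SD) | λ | ANOVA rejects, either pattern | Kruskal-Wallis, (d, d, 0) | Kruskal-Wallis, (d, 0, 0) |
|---|---|---|---|---|
| 0.1 | 0.20 | 0.065 | 0.064 | 0.064 |
| 0.2 | 0.80 | 0.113 | 0.105 | 0.107 |
| 0.3 | 1.80 | 0.201 | 0.189 | 0.193 |

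The Kruskal-Wallis columns use 50,000 simulations of normal data each. By symmetry they are equal; the gaps are simulation error.

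**What a named contrast would deliver.**
- Difference in mean change between two arms: 95% half-width = t(0.975, 87) × √(2/30) = 1.988 × 0.258 = 0.513 SD.
- Hodges-Lehmann shift, normal data, 30 versus 30, 10,000 simulations: mean half-width 0.531 SD, coverage 0.954.
- Pooled SD, already available from the ANOVA: √(87/χ²(0.975, 87)) = 0.871 and √(87/χ²(0.025, 87)) = 1.174, so the 95% interval runs from 0.87 to 1.17 times the estimate.

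**Outcome 3, no difference between Groups 1 and 2.** Pearson chi-square, exact enumeration of all outcomes with 30 per arm, asymptotic 5% cutoff, true click rate 30% in Groups 1 and 2:

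| Recycling link, Group 3 | Three-group test rejects |
|---|---|
| 30% | 0.052 |
| 20% | 0.132 |
| 10% | 0.480 |
| 50% | 0.367 |

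Group 1 versus Group 2 alone rejects 0.049 of the time.

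**Precision of Group 1 minus Group 2 for clicks.** At equal observed rates p with Wilson limits l and u, the Newcombe half-width is √[(p − l)² + (u − p)²]. At 9/30, l = 0.167 and u = 0.479, giving √(0.133² + 0.179²) = 0.223. At 3/30, 6/30 and 15/30 it is 0.169, 0.202 and 0.238. The Wald half-widths at 3/30, 6/30, 9/30 and 15/30 are 0.152, 0.202, 0.232 and 0.253. Newcombe is preferred because Wald can under-cover at low rates: at true rates of 10% versus 5%, exact coverage is 0.930 for Wald and 0.981 for Newcombe.

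**The case against.** This is a pilot meant to produce estimates. The plan has no rule that credits the module on a significant test, and a fitted ANOVA already contains the three means and the pooled SD, so any contrast can be computed afterwards. That stands, and it narrows the point on outcomes 1 and 2 to one of pre-specification. Being able to compute a difference later does not settle beforehand which difference answers Aim 2.

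The choice of Group 1 minus Group 2 can also be disputed. Aim 2 names no comparator, so Group 1 minus Group 3 is a fair reading too. The document does not say that Group 2 receives no tailored content, and Section 1 says the parent project is to "test the efficacy of a patient-centered, tailored message intervention for increasing CRC screening". This stands in part. Group 1 minus Group 2 is closest to Aim 2 because the project adds a nutrition module to an existing intervention, but it cannot be labelled the effect of tailoring on present evidence. Both contrasts should be reported.

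For outcome 3, the three-group reading is not stated and the click rates are assumptions. Both points are right. The rejection rates show what can happen, not what is likely. What Group 3 is offered is also unsettled: Pilot Test Structure sends participants who choose additional information to cancer prevention resources, with no group excluded, while the outcome 3 example gives Group 3 a recycling link. Those statements need reconciling, but they do not make a comparison across different links valid.

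**Conclusion.** The concern holds and should be fixed before data are seen. No between-arm difference is specified for any Aim 2 outcome.

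For outcomes 1 and 2, the named tests give the same rejection rate (6% to 20% over the plan's effect range) whether or not the new module adds anything to the current one. The loss is a pre-specified estimate for the larger trial; the SD of change is not lost.

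For outcome 3, a three-group test can reject well above 5% with no difference between Groups 1 and 2 (13% to 48% in the cases shown where the recycling rate differs from 30%). This is conditional on the three-group reading and on the assumed click rates.

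Confidence is high that no contrast is named and that the links differ by arm. The finding does not say that 30 per arm is too few for a pilot.

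**What to change.** **Outcomes 1 and 2.**
- Pre-specify Group 1 minus Group 2 in mean change, with 95% confidence interval and pooled SD. Label it as the high interactive nutrition module against the current low interactive module. Call it the effect of tailored feedback only if the sponsor confirms that Group 2 receives none.
- Report Group 1 minus Group 3 with 95% confidence interval as the whole-package effect.
- Keep the omnibus test as supportive.
- If the Kruskal-Wallis branch is used, give the Hodges-Lehmann shift with 95% confidence interval for the same two pairs.

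**Outcome 3.**
- State the groups compared. Compare Groups 1 and 2 only, separately for the diet link and the FIT link, as a risk difference with a Newcombe 95% confidence interval.
- Report Group 3's recycling clicks descriptively.
- Reconcile the statements on what Group 3 is offered.

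Describe all of these as planning estimates, not efficacy tests.

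**Cost.** Wording only, with the same data and sample size. The contrasts come from the same ANOVA model; the rank-based branch adds one interval procedure. The downside is a few more reported contrasts and wide intervals: about ±0.51 to 0.53 SD, wider than the plan's own .1 to .3 range, and about ±17 to 24 percentage points for clicks. They will not settle whether the module works.

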- Sample size was determined using a stepped rule of thumb based on an expected small effect size and 90% power for the future trial (Bell, Whitehead, & Julious, 2018). Based on this approach, if we expect a small effect size (.1-.3) at 90% power (for the larger trial) the pilot would require n=25 per arm to obtain estimates to inform larger trials sample size. Thus, n=30 per arm (N =90) is expected to give appropriate estimates to inform the larger trial.
- Data will be de-identified, stored with participant IDs on UF secure server accessible from PI's password protected computer, and analyzed using quantitative data analysis software for, preliminary estimates to plan a larger trial (e.g. confidence interval estimates, recruitment/response rates) and descriptive statistics to describe participant characteristics.
- Descriptive statistics will be calculated for all variables including mean, standard deviation, median, inter-quartile range, minimum and maximum for

continuous variables and frequency and proportion for categorical variables. Graphical illustration will be provided if applicable.

- Data analytics obtained from wix.com will be reviewed to understand use. Descriptive statistics on resources clicked and time spent on the site will be calculated.

4. Possible Discomforts and Risks:

- There are no potential risks of physical, psychological or economic harm associated with participant in this study.

5. Possible Benefits:

- While no direct benefits are expected, participants may benefit from learning about their health and ways to engage in health prevention behaviors relevant to nutrition and cancer screening.
- The risks to subjects are reasonable in relation to the anticipated benefits due to the importance of the knowledge that will be gained from this research to benefit future populations.

6. Conflict of Interest:

- There are no real or potential conflicts of interest with any investigators with regard to this specific research project.

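### Adjusting the post-test score for baseline is expected to give narrower intervals for outcomes 1 and 2 than the planned ANOVA on change, at no data cost; the gain may be small

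*Combined protocol and SAP*

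**What the plan says.** Section 3, Aim 2, describes a "3-group randomized design with 30 participants per group". Outcomes 1 and 2 are scores built from 7-point Likert items. For both, under Data and analysis, the plan is "one-way ANOVAS or Kruskal-Wallis test on the difference between baseline and post-test to obtain estimates to inform the larger trial". Taking a difference requires a baseline score for every analysed participant, so the covariate is already being collected. Nothing in the document plans to adjust for it.

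The same section states what the pilot is for: "preliminary estimates to plan a larger trial (e.g. confidence interval estimates, recruitment/response rates". It does not say which quantities will have intervals. It also plans summary statistics: "Descriptive statistics will be calculated for all variables including mean, standard deviation, median", with further measures listed. The correlation between baseline and post-test is not named.

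On timing, the Pilot Test Structure says "Each module will be approximately 5-10 minutes". It does not say how soon after the module the post-test is taken.

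**The concern.** ANOVA on change fixes the slope of post-test on baseline at 1. A model with baseline as a covariate estimates that slope. Under randomisation both target the same arm difference without bias, so the issue is precision only. If the true slope is not 1, the change score carries avoidable variance.

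The pilot's product is estimates. If its arm-difference intervals for outcomes 1 and 2 come from the ANOVA on change, they are expected to be somewhat wider than the same 90 participants allow. The effect anticipated for the larger trial is small (standardised 0.1 to 0.3), and intervals at 30 per arm are wide against that range, so precision that costs nothing is worth having. The point does not bear on the power or the size of the larger trial.

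**Working it through.** **The plan's own figure.** 3 arms × 30 = 90, which agrees with the stated total. The 25 per arm behind it is read from a cited rule of thumb and cannot be recomputed from the document. This point does not affect it.

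**Inputs from the document.** Three randomised arms of 30; change from baseline analysed without a covariate.

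**Inputs assumed, because the document gives none.** The correlation r; the ratio q of post-test SD to baseline SD; two-sided 95% intervals; no dropout; the same r and SDs in every arm.

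**Variances.** With baseline SD s0 and post-test SD s1:

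- change score: s0² + s1² − 2·r·s0·s1
- post-test adjusted for baseline: s1²·(1 − r²)
- difference: (s0 − r·s1)²

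The difference is never negative. It is zero only when the slope r·s1/s0 equals 1.

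Put s1 = 1 and s0 = 1/q. Then V_change = 1 + 1/q² − 2r/q and V_adj = 1 − r². At q = 1 and r = 0.5, V_change = 1.00 and V_adj = 0.75, a difference of 0.25 = (1 − 0.5)².

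**Expected half-width for a difference between two arms.**

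- change: t(87)·√(2·V_change/30)
- adjusted: t(86)·√(2·V_adj·(1 + 1/85)/30)

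Here t(87) = 1.9876 and t(86) = 1.9879. The factor 1 + 1/85 is the average price of chance baseline imbalance. At q = 1 and r = 0.5:

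- change: 1.9876 × √(2 × 1.00/30) = 0.513
- adjusted: 1.9879 × √(2 × 0.75 × 1.01176/30) = 0.447
- ratio 0.871, so 13% narrower

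**Equal SDs (q = 1), in post-test SD units.**

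| r | change | adjusted | narrower by |
|---|---|---|---|
| 0.3 | 0.607 | 0.493 | 19% |
| 0.5 | 0.513 | 0.447 | 13% |
| 0.7 | 0.398 | 0.369 | 7% |
| 0.9 | 0.230 | 0.225 | 2% |

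**Unequal SDs, percentage narrower.**

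| q | r = 0.3 | r = 0.5 | r = 0.7 | r = 0.9 |
|---|---|---|---|---|
| 0.8 | 29% | 24% | 20% | 22% |
| 1.2 | 12% | 6% | 1% | 0.6% |
| 1.25 | 11% | 5% | 0.4% | 2% |

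**Where the gain disappears.** At slope 1 the two variances are equal and only the small-sample cost remains: (t(86)/t(87))·√(1 + 1/85) = 1.0060, an expected widening of 0.6%. This happens at q = 1.25 and r = 0.8, where both variances are 0.36. With equal SDs the width ratio is 1.0060·√((1 + r)/2), which reaches 1 at r = 2/1.0060² − 1 ≈ 0.976.

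**Simulation.** With 20,000 bivariate normal pilots per setting, mean half-widths at equal SDs were 0.606/0.491, 0.512/0.446, 0.396/0.368 and 0.229/0.225, in line with the formulas. Coverage was 94.7-95.2% for both methods. The adjusted interval was the narrower one in 98% of pilots at r = 0.7 and 77% at r = 0.9. At q = 1.25 and r = 0.8 it was narrower in only 20%.

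A separate run of 3,000 pilots per setting used scores rounded and capped to a 1-7 scale. For underlying correlations of 0.3 to 0.9 the ratio of adjusted to change half-width ran from 0.801 to 0.966, with coverage of about 94-95% for both methods.

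**The case against.** The strongest reply is that nothing is broken and the benefit is unknown. The change-score analysis is coherent and unbiased. The gain rests wholly on assumed inputs and runs from 29% to slightly negative. The larger figures need a low r or a post-test SD that shrinks, and nothing in the document supports either. A post-test soon after a short module points to high r. All of this stands and limits the point to a suggestion. Because the timing is not stated, low r cannot be excluded either.

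The link to planning can also be questioned. Sizing a trial mainly needs an SD, and adjustment does not make an SD estimate relatively more precise (86 against 87 degrees of freedom). That is right. Much of what is needed could also be recovered: if the change score is among the variables summarised, r = (s0² + s1² − s_change²)/(2·s0·s1). Reporting r directly is therefore a convenience, but a useful one, because the plan does not say that the change score will be summarised.

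The calculations assume a common r and common SDs across arms, yet the control arm sees an unrelated module. In a simulation with r = 0.5 in the two intervention arms and 0.95 in the control arm (equal SDs, 8,000 runs), coverage for Group 1 against Group 2 fell to about 90% for change and 91% for the adjusted model. The adjusted interval was still about 9% narrower. The weakness is shared by both methods and does not reverse the comparison, but a single residual SD should then be read with care.

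Finally, Kruskal-Wallis is an equal option in the plan and gives a test, not an interval. The width comparison does not apply to it.

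**Conclusion.** The point holds as an expected, often small, efficiency gain. It is not an error in the plan. Over r = 0.3 to 0.9 with equal SDs, the adjusted interval is expected to be 19% down to 2% narrower. If r is high, as it may be when the post-test follows the module directly, the equal-SD gain is about 2-7%. With a post-test SD 20-25% above baseline and r of 0.7 to 0.9, the result lies between a 0.6% loss and a 2% gain.

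The gain is an average and is not assured in a single data set. It rests on assumed r and SDs, 30 complete participants per arm, two-sided 95% intervals and common variances across arms, and it concerns the ANOVA option only. The case for the change is that the downside is bounded at 0.6% in expectation.

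**What to change.** For outcomes 1 and 2, estimate the arm differences with 95% confidence intervals from a linear model of post-test score on arm and baseline score. Report the residual SD, the SDs of baseline, post-test and change, and the baseline to post-test correlation, so that the larger trial can be sized under either analysis. Reporting the SDs and the correlation by arm as well would show whether the common-variance assumption is reasonable. Keep change scores as a descriptive summary and Kruskal-Wallis on change as a sensitivity analysis.

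The cost is a few lines of analysis-plan wording and one residual degree of freedom out of 87. No new data are needed.
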